2.4.2 Power calculation for secondary endpoints

The assumptions for power calculations of the secondary endpoints included in the hierarchy and for which supporting data are available, in the TNF α -IR population are based on the results of PA0008 and the SPIRIT-P2 studies. All power calculations for binary endpoints were performed using a 2-sided 2-sample Chi-square test with continuity correction (Fleiss et al, 1980). All power calculations for continuous endpoints were performed using a 2-sided 2-group Satterthwaite t-test (Moser et al, 1989).

For the change from Baseline in HAQ-DI at Week 16, based on data from the TNF α -IR population in SPIRIT-P2 Week 12 as well as Week 12 and Week 16 data from the PA0008 and PsA001 studies respectively, estimates of the SD in the active treatment and placebo groups are 0.71. A two-group Satterthwaite t-test with a 0.050 2-sided significance level will have 85% power to detect a difference of 0.23 in the mean change from Baseline in HAQ-DI at Week 16 between BKZ treatment and placebo assuming a sample size of 390 subjects randomized 2:1.

For PASI90 response at Week 16, a PASI90 response at Week 12 of 38% (N=122), from the SPIRIT-P2 study is assumed. The PASI90 response at Week 12 in the BKZ 160mg group is 50.0% (n=8) in the subgroup analysis of the TNF α -IR patients. Placebo PASI90 response at Week 16 is based on SPIRIT-P2 data (6.0% at Week 12). However, for this endpoint the placebo response is rounded to 10%. With those assumptions, the endpoint has 99% power to detect a treatment difference of 28% (OR of 5.52) at an assumed 50% of subjects with BSA \geq 3% of the planned sample size.

For the change from Baseline in PCS score of SF-36 at Week 16, based on data from the TNF α -IR population in SPIRIT-P2 where estimates of the SD in the active treatment and placebo groups at Week 12 are ixekizumab Q4W (SD=11.95) and placebo (SD=12.15). A 2-group Satterthwaite t-test with a 0.050 2-sided significance level will have 89% power to detect a

difference in means of 4.4 change from Baseline in SF-36 PCS score at Week 16 between the bimekizumab and placebo treatment groups with a sample size of 390 subjects randomized 2:1.

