4 STATISTICAL/ANALYTICAL ISSUES

4.1 Adjustments for covariates

The primary efficacy analysis will investigate the treatment effect, adjusting on the 2 randomization stratification variables:

- Region
 - North America, Western Europe, Eastern Europe, Asiaor
 - North America, Eastern Europe, Western Europe + Asia if the percentage of randomized subjects is less than 10% in either of the Asia or Western Europe regions

- Prior TNF α inhibitor exposure (inadequate response to 1 prior TNF α inhibitor, inadequate response to 2 prior TNF α inhibitors, intolerance to TNF α inhibitors)

When adjusting on these 2 variables, a statistical model might not converge (ie, in case the likelihood maximization algorithm failed to converge). In that case, the statistical model will be run after dropping stratification variables in their order of appearance, successively region (one first and the other after) and prior TNF α inhibitor exposure.

In the event that a subject is stratified in the incorrect stratum (ie, the stratum recorded in the Interactive voice or web Response System (IXRS) differs from the actual stratum the subject belongs to), the actual stratum will be used for the analysis.

The secondary analyses will be adjusted on the same categorical factors as the primary analysis. For continuous variables, Baseline value (of the variable of interest) will also be included as covariate where appropriate.

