8.1.2 Primary analysis of the primary efficacy variable

The primary efficacy variable will be analyzed for all subjects in the RS.

The primary endpoint is the ACR50 response at Week 16. The primary efficacy analysis will evaluate the composite estimand in the RS. The composite estimand combines the clinically meaningful improvement from Baseline in ACR components as assessed using the ACR50 response at Week 16 and not discontinuing study treatment prior to Week 16.

The following 4 attributes describe the estimand that will be used to define the treatment effect of interest for the primary efficacy analysis:

- Population = Subjects enrolled according to the protocol-specified inclusion/exclusion criteria and randomized to IMP
- Subject-level outcome = ACR50 at Week 16
- Intercurrent event handling = An intercurrent event is defined as discontinuation of study treatment prior to Week 16. A composite strategy will be implemented in which a positive clinical outcome is defined as achieving ACR50 at Week 16 and not discontinuing study treatment through Week 16.
- Population-level summary measure = Conditional odds ratio comparing BKZ to placebo and difference of response rate between BKZ and placebo.

Missing data at Week 16 that are not preceded by an IE and any data after an IE will be imputed as non-responders. This results in a more traditional NRI approach and will be labeled as such throughout the SAP.

The statistical hypothesis for the ACR50 response at Week 16 is that the conditional OR for ACR50 response in the BKZ treatment compared to placebo treatment is equal to 1.

A logistic regression model will be used to assess the treatment effect on ACR50 response at Week 16. The model will include fixed effects for treatment, and prior TNF α inhibitor exposure and region as stratification factors. The suitability of including these variables in the model will be assessed using Pearson and Deviance and the Hosmer-Lemeshow Goodness-of-Fit Tests (Hosmer and Lemeshow, 2000).

P-values below 0.05 would lead to a reconsideration of the model to be used and if the logistic regression model is unable to converge the stratification variables will be dropped ([Section 4.1](#)). In that case, all supportive analyses as well as imputation models conducted for the primary endpoint will disregard these exploratory factors from their models.

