The country-specific analyses performed on subjects randomized in Japan will not consider the region factor as a covariate for the modelling. Considering that the number of subjects randomized in Japan is low (less of 10% of the RS), statistical models might not converge. If a model (logistic Model or mixed model) is not converging, all related adjusted statistics and p-value will not be presented; “NE” for “Not Evaluable” will be displayed instead.

The SAS® PROC LOGISTIC will be used to run the logistic regression.

The summary table results will present the adjusted responder rates and the associated 95% CI for BKZ and placebo, the adjusted odds ratio and 95% CI for the comparison of BKZ versus placebo, and the p-value that the OR=1 and the difference of response rate between BKZ and placebo and associated 95% CI. The treatment comparison will be made using the 2-sided Wald test at a significance level of $\alpha=0.05$ (ie, H_1 in [Table 7-4](#)).

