8.2.2 Primary analysis of secondary efficacy variables

The secondary efficacy variables will be analyzed for all subjects in the RS.

As indicated in [Table 7-4](#), there are 4 secondary endpoints included in the testing hierarchy that will be tested in a chronological order until one is failed to be statistically significant.

For the other secondary endpoints (which are not part of the testing hierarchy), the p-values produced by the statistical models will be considered nominal since these endpoints are not controlled for multiplicity.

For the secondary composite and non-composite binary endpoints, the same estimand structure (composite estimand) as the one defined for the primary efficacy analysis of the primary efficacy endpoint ([Section 8.1.2](#)) will be used. The NRI approach for handling missing data and the same analysis model will be considered, and the analysis results will be presented similarly.

The statistical hypothesis for the binary variables at Week 16 is that the conditional odds ratio in the BKZ group compared with placebo treatment group is equal to 1. For the secondary continuous endpoints, the analysis will evaluate the hypothetical estimand as defined below:

- Population = Subjects enrolled according to the protocol-specified inclusion/exclusion criteria and randomized to IMP.
- Subject level outcome = variable as stated in [Section 2.2.2](#)
- Intercurrent event handling = An intercurrent event is defined as discontinuation of study treatment prior to Week 16. A hypothetical strategy for addressing intercurrent events will be implemented. This estimand targets the treatment difference in a scenario where withdrawal from study treatment does not occur, such that outcomes for subjects without an IE are as observed, and outcomes for subjects with an IE are treated as though they had completed treatment through Week 16 but on placebo. A MI strategy will be used to impute any missing data and observed data after IE which will be set to missing prior to running MI. Such data will be imputed using Reference-Based MI, in which the MI model is based on data from the placebo group.
- Population-level summary measure = the difference in the adjusted means between BKZ 160mg Q4W and placebo.

The same analysis model and imputation strategy for handling missing data as in [Section 8.1.4.4](#) will also be considered. The analysis results will be presented similarly as for this analysis on the individual ACR components.

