8.3.2.3 Additional statistical analysis for other efficacy endpoints

Although statistical testing is not planned for other efficacy variables as per protocol, for selected other efficacy variables, it is of interest to perform statistical testing and calculate inferential statistics. The associated p-values will be considered nominal and not controlled for multiplicity.

For continuous variables, the MI-MCMC/monotone regression approach will be applied for the imputation model on the change from Baseline (hypothetical estimand). The analysis model will be based on ANCOVA with fixed effect of treatment, region, and prior TNF α inhibitor exposure and Baseline value as covariates.

For responder variables, the analysis will follow the NRI approach (composite estimand). The analysis model will be based on a logistic model with fixed effect for treatment and prior TNF α inhibitor exposure at Baseline and region as stratification variables.

Below is a list of other secondary efficacy variables for which these nominal p-values (with the timepoints in parentheses) will be calculated.

The results of these inferential tests (LSM differences for continuous variables, OR for binary variables, along with 95% CI and p-value) will be presented in a single table:

For the following endpoints, the p-value provided (based on the change from Baseline for continuous variables) will be based on the comparison of the 2 treatment groups using the same statistical methods for binary variables as used for the primary analysis of ACR50 (Section 8.1.2) and for continuous variables as used for the analysis of ACR components (Section 8.1.4.4):

- ACR20/50/70 (Week 4, 8, 12, 16)
- PASI75/90/100 (Week 4, 8, 12, 16)
- ACR50/PASI90 composite (Week 4, 8, 12, 16)
- ACR50/PASI100 composite (Week 4, 8, 12, 16)
- TJC (Week 4, 8, 12, 16)
- SJC (Week 4, 8, 12, 16)
- MDA (Week 4, 8, 12, 16)
- PtAAP (Week 4, 8, 12, 16)
- PsAQoL (Week 4, 12, 16)
- PsAID-12 (Week 4, 12, 16)
- FACIT-Fatigue subscale (Week 4, 12, 16)
- WPAI-SHP (Week 12, 16) (on observed data)
- DAPSA (Low Disease Activity or better) “response” (Week 4, 8, 12, 16)
- PsARC Response (Week 4, 8, 12, 16)

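### The logistic Wald test has no rule for an arm with zero responders, and the planned fallback of dropping strata cannot repair it; the exposure is mainly in sparse nominal endpoints

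*SAP*

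**What the plan says.** Section 8.1.2 fits a logistic model for ACR50 at Week 16 with treatment, prior TNFα inhibitor exposure and region, and specifies the test: "The treatment comparison will be made using the 2-sided Wald test at a significance level of" 0.05. The null hypothesis is a conditional odds ratio of 1.

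The same test reaches the other binary endpoints in two ways. For the secondary endpoints, Section 8.2.2 says: "The NRI approach for handling missing data and the same analysis model will be considered, and the analysis results will be presented similarly". That covers PASI90 and IGA response at Weeks 4 and 16, MDA, ACR20 and ACR70. Section 8.3.2.3 applies the Section 8.1.2 method to a further list at Weeks 4 to 16. The list includes PASI75/90/100, the ACR50/PASI90 composite and "ACR50/PASI100 composite (Week 4, 8, 12, 16").

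On non-convergence, Section 8.1.2 says that "if the logistic regression model is unable to converge the stratification variables will be dropped". Section 4.1 says that "the statistical model will be run after dropping stratification variables in their order of appearance", region first and prior TNFα exposure second. The instruction that "all related adjusted statistics and p-value will not be presented" stands in the paragraph on the Japan-only analyses. A poor goodness-of-fit result leads to a reconsideration of the model, with no method named. The SAP names no exact, score, likelihood-ratio or penalised test, and has no rule for an arm without responders.

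**The concern.** If one arm has no responders, the outcome is separated by treatment. The maximum-likelihood treatment coefficient runs off to infinity and its standard error grows faster, so the Wald ratio falls towards zero. The strongest possible contrast then yields a non-significant p-value and an unusable odds ratio and interval. Dropping region and prior TNFα exposure does nothing, because the separation lies in the treatment term and remains in a treatment-only model.

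For the nominal endpoints this would put a meaningless p-value in the Section 8.3.2.3 table, which lists only odds ratio, confidence interval and p-value. At H3 it would also stop the fixed sequence in Section 4.5, so SF-36 PCS (H4) and MDA (H5) could not be formally tested. Without a written rule, the team would have to report that result or pick another test after unblinding.

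**Working it through.** **Inputs from the SAP.** Arms of 260 and 130 (Section 2.4). ACR50 26% vs 10% (2.4.1). PASI90 38% on active; for placebo, "Placebo PASI90 response at Week 16 is based on SPIRIT-P2 data (6.0% at Week 12"), then rounded to 10% for planning; half the subjects assumed to have BSA ≥3%, hence 130 vs 65 (2.4.2). MDA 5% on placebo plus a 12-point difference, hence 17% vs 5%.

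**Reproducing the plan's figures.** The continuity-corrected chi-square formula gives 96.6% power for ACR50 (stated 96%), 99.1% for PASI90 (stated 99%) and 92.5% for MDA (stated 92%). The planning figures hold for the test they were computed with.

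**Mechanism, treatment-only model.** With x of 130 responders on BKZ and y of 65 on placebo:

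- β = ln[x/(130−x)] − ln[y/(65−y)]
- SE = √[1/x + 1/(130−x) + 1/y + 1/(65−y)]

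As y approaches 0, β grows like −ln y but SE grows like 1/√y, so β/SE tends to 0.

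- 26/130 vs 1/65: β = −1.386 + 4.159 = 2.773; SE = √(0.0385 + 0.0096 + 1 + 0.0156) = 1.031; z = 2.69; p = 0.007.
- 26/130 vs 0/65: no finite β. Wald p is 0.53, 0.97 and 0.9997 after 8, 15 and 25 Newton steps. Fisher p = 0.00002. Firth's estimate is OR = (26.5/104.5)/(0.5/65.5) = 33, with penalised likelihood-ratio p = 0.000009.
- 50/130 vs 0/65: Fisher p = 3×10⁻¹¹. Wald p is 0.90 to 1.00 at gradient tolerances of 10⁻⁶ to 10⁻¹². It falls below 0.05 only if the iteration is cut off after about five steps, far from convergence. The value therefore reflects the stopping rule, not the data.

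**Does the fallback help?** In simulated data at 38% vs 0% (stratum shares assumed), the median Wald p was 0.989 with all strata, 0.989 without region and 0.989 with treatment only.

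**Chance of an empty placebo cell, (1−p)ⁿ.**

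- ACR50: 0.90¹³⁰ = 0.0001%
- MDA: 0.95¹³⁰ = 0.13%
- PASI90 Week 16 (H3): 0.90⁶⁵ = 0.11%; at the source rate, 0.94⁶⁵ = 1.8%
- Sparse endpoints in 65 subjects, assumed rates: 0.6% gives 68%, 1% gives 52%, 2% gives 27%, 6% gives 2%

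The 0.6% is 10% × 6%, treating ACR50 and PASI90 as independent. The 6% is the ceiling for the ACR50/PASI90 composite at the source rate, since it cannot exceed either component.

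**Power, exact enumeration of two binomials (130 vs 65), treatment-only model, two-sided 0.05.** The hybrid is Wald, replaced by the Firth penalised likelihood-ratio test when an arm is empty or full.

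| BKZ vs placebo | Wald | Hybrid |
|---|---|---|
| 9.9% vs 0.6% (26% × 38%; 10% × 6%) | 9% | 73% |
| 20% vs 1% (assumed) | 47% | 99.5% |
| 20% vs 2% (assumed) | 71% | 98% |
| 38% vs 6% (H3, source rate) | 98.2% | 100.0% |
| 38% vs 10% (H3, planning rate) | 99.3% | 99.4% |

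**Type I error of the hybrid.** At common response rates of 0.6%, 1%, 2%, 5% and 10% it rejects 0.3%, 0.8%, 1.6%, 3.7% and 3.9% of the time.

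**Subgroups.** For PASI90 by subgroup (Sections 4.8 and 8.2.3), a category with 10 placebo subjects has no responder with probability 0.94¹⁰ = 54% at the 6% rate, and 35% at 10%. With 20 subjects the figures are 29% and 12%. The category sizes are assumed.

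**The case against.** The quoted sentence governs ACR50, where an empty arm is practically impossible. In the hierarchy only H3 is at any risk, between 0.11% and 1.8% on the SAP's own figures. The endpoints more likely to be affected carry nominal p-values without multiplicity control (Sections 8.2.2 and 8.3.2.3). All of this stands and limits the weight of the point.

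A reader might infer that an empty placebo arm is the likely outcome for the composites. The documents do not support that. The 68% rests on independence, yet non-responder imputation turns a discontinuation into non-response on both components, which induces dependence. At the component ceiling the chance is 1.8% at a 6% PASI90 rate and 0.11% at 10%. The SAP gives no placebo rate for PASI100 or any Week 4 skin endpoint.

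A reader might also infer that a strong effect would be reported as no difference. That is too strong. Section 8.3.2.2 tabulates responder numbers and proportions by visit and plots the ACR and PASI responses, and Sections 8.1.2 and 8.2.2 show the rate difference with its interval. For 50/130 vs 0/65 that difference is 38 points (delta-method 95% CI about 30 to 47), visibly at odds with the p-value. Only the Section 8.3.2.3 table lacks such a check.

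Finally, a hybrid rule jumps at its boundary: 13/130 vs 0/65 gives a Firth p of 0.004, while 13/130 vs 1/65 gives a Wald p of 0.06. That is a fair criticism, but the rule still improves on a test that cannot reject at all.

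**Conclusion.** The point holds within these limits. Followed as written, the plan returns a non-significant Wald test whenever a treatment arm has no responders, and its stated remedy cannot change that. ACR50 and MDA are essentially unaffected. H3 is exposed with probability 0.11% to 1.8%, and the consequence there, loss of H4 and H5, would be serious. The practical exposure is in Week 4 PASI90 and IGA, PASI100, the two ACR50/PASI composites and small PASI90 subgroup categories. The power loss there runs from slight to most of the power, depending on placebo rates that the SAP does not state.

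The power and error figures assume the planned 130 vs 65 split and a model without strata. The mechanism needs neither assumption.

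**What to change.** Keep the Wald test as the default. Before unblinding, add to Sections 4.1 and 8.1.2: *If a treatment group has no responders, or only responders, the logistic model with the same covariates will be fitted by Firth's penalised likelihood. The p-value will come from the penalised likelihood-ratio test and the 95% CI for the odds ratio from the profile penalised likelihood. Observed response rates will be shown with an exact CI for their difference. Dropping stratification factors does not apply in this case.* State that the rule covers H3, the other binary secondary endpoints and the binary endpoints in Section 8.3.2.3.

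The likelihood-ratio p-value should be named explicitly: for 20/130 vs 0/65 it is 0.0002, against 0.028 for a Wald test on the Firth fit.

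Firth should not be extended to every Section 8.3.2.3 endpoint. That list includes ACR50, PASI90 and MDA at Week 16, which are H1, H3 and H5, and each would acquire a second, conflicting p-value.

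The cost is one paragraph and a standard option in the logistic procedure, with no patients, visits or alpha. The downside is a second estimator for the few affected endpoints. Type I error stays at or below about 3.9% at null rates of 0.6% to 10%.

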8.1.3 Subgroup analyses of the primary efficacy variable

Subgroup analyses will be performed on the primary efficacy variable on the RS.

The variables for subgroup analyses are defined in [Section 4.8](#).

For each subgroup analysis (except for the analysis by prior TNF α exposure, by region, and by ADA b status), a logistic regression will be fitted involving the same terms that were retained when running the primary analysis model, plus a term for the subgroup and the subgroup by treatment interaction as detailed below:

- Fixed effect for treatment
- Prior TNF α 1 (1 for inadequate response to at least 1 prior TNF α inhibitor)
- Prior TNF α 2 (1 for inadequate response to 2 prior or more TNF α inhibitors)
- Region
- Term for subgroup
- Terms for subgroup by treatment interaction(s).

For subgroup analyses by Prior TNF α exposure, the terms that will be retained will be:

- Fixed effect for treatment
- Prior TNF α 1 (1 for inadequate response to 1 prior TNF α inhibitor)
- Prior TNF α 2 (1 for inadequate response to 2 prior TNF α inhibitors)
- Region
- Terms for Prior TNF α inhibitor exposure by treatment interaction

For subgroup analyses by region, the terms that will be retained will be:

- Fixed effect for treatment
- Prior TNF α 1 (1 for inadequate response to 1 prior TNF α inhibitor)
- Prior TNF α 2 (1 for inadequate response to 2 prior TNF α inhibitors)
- Region
- Terms for region by treatment interaction

For subgroup analyses by ADA b status, the terms that will be retained will be:

- prior TNF α exposure at Baseline
- Region
- ADA b Status (Positive, Negative)

For all subgroup analyses, the terms for the subgroups will be coded as below:

- For Yes/No or positive /negative variables, the category “yes” or “positive” will be coded “1”.
- For continuous variables in 2 classes, the highest category will be coded “1”.
- For continuous variables in 3 classes (or more), 2 (or more) binary variables will be created and coded “1” for the 2 (or more) top categories.

- For gender, “male” will be the category coded “1”.

The same estimand approach as the one used for the primary analysis will be used to handle missing data (NRI).

For each subgroup category and each treatment group (subgroup analysis on the ADA_b status for only BKZ group), the mean proportion of responders on imputed datasets, the adjusted responder rates with associated 95% CI will be provided. The adjusted OR (for the comparison BKZ and placebo) and the corresponding 95% CI will also be provided. In addition, the difference in response rates between BKZ and placebo and the corresponding 95% CI will also be presented (except for the subgroup analysis on the ADA_b status). The results obtained for each subgroup will be presented in one single table. The ORs and associated 95% CIs for each subgroup category will also be displayed on a single forest-plot.

The observed rates of responses by subgroup categories will be also provided along with the results obtained on imputed data.

In addition, the mean proportion of ACR50 responders at Week 16 separated by the 6 pre-defined ADA_b subcategories (as defined in [Section 9.2](#)) will be presented graphically for the BKZ-randomized subjects.

